11.3 Subject Population(s) for Analysis

Efficacy analysis will be performed on ITT basis. Any subject randomized into the study, regardless of whether they received study drug will be included into the analyses.

11.4 Data Management

A computerized data entry and management system will be developed during the initial project months that will enter all study data. All data will be entered using data entry programs.

12 ADVERSE EXPERIENCE REPORTING AND DOCUMENTATION

12.1 Adverse Events

Definitions: Unanticipated Problems Involving Risk to Subjects or Others

Any incident, experience, or outcome that meets all of the following criteria:

- Unexpected in nature, severity, or frequency (i.e. not described in study-related documents such as the protocol or consent form and the patient information sheets)
- Related or possibly related to participation in the research (i.e. possibly related means there is a reasonable possibility that the incident experience, or outcome may have been caused by the procedures involved in the research)
- Suggests that the research places subjects or others at greater risk of harm (including physical, psychological, economic, or social harm).

Adverse Event

An **adverse event (AE)** is any symptom, sign, illness or experience that develops or worsens in severity during the course of the study. Intercurrent illnesses or injuries should be regarded as adverse events. Abnormal results of diagnostic procedures are considered to be adverse events if the abnormality:

- results in study withdrawal
- is associated with a serious adverse event
- is associated with clinical signs or symptoms
- leads to additional treatment or to further diagnostic tests
- is considered by the investigator to be of clinical significance

AE Severity

Table 1: below should be used to grade severity. It should be pointed out that the term “severe” is a measure of intensity and that a severe AE is not necessarily serious.

Table 1. AE Severity Grading

Severity (Toxicity Grade)	Description
Mild (1)	Transient or mild discomfort; no limitation in activity; no medical intervention or therapy required. The subject may be aware of the sign or symptom but tolerates it reasonably well.
Moderate (2)	Mild to moderate limitation in activity, no or minimal medical intervention/therapy required.
Severe (3)	Marked limitation in activity, medical intervention/therapy required, hospitalizations possible.
Life-threatening (4)	The subject is at risk of death due to the adverse experience as it occurred. This does not refer to an experience that hypothetically might have caused death if it were more severe.

AE Relationship to Study Drug

The relationship of an AE to the study drug should be assessed using the following the guidelines in Table 2.

Table 2. AE Relationship to Study Drug

Relationship to Drug	Comment
Definitely	Previously known toxicity of agent; or an event that follows a reasonable temporal sequence from administration of the drug; that follows a known or expected response pattern to the suspected drug; that is confirmed by stopping or reducing the dosage of the drug; and that is not explained by any other reasonable hypothesis.
Probably	An event that follows a reasonable temporal sequence from administration of the drug; that follows a known or expected response pattern to the suspected drug; that is confirmed by stopping or reducing the dosage of the drug; and that is unlikely to be explained by the known characteristics of the subject's clinical state or by other interventions.
Possibly	An event that follows a reasonable temporal sequence from administration of the drug; that follows a known or expected response pattern to that suspected drug; but that could readily have been produced by a number of other factors.
Unrelated	An event that can be determined with certainty to have no relationship to the study drug.

12.2 Serious Adverse Experiences (SAE)

An SAE is defined as any AE occurring at any dose that results in any of the following outcomes:

- death
- a life-threatening adverse experience
- inpatient hospitalization or prolongation of existing hospitalization
- a persistent or significant disability/incapacity
- a congenital anomaly/birth defect

Other important medical events may also be considered an SAE when, based on appropriate medical judgment, they jeopardize the subject or require intervention to prevent one of the outcomes listed. Important medical events are those that may not be immediately life threatening, but are clearly of major clinical significance. They may jeopardize the subject, and may require intervention to prevent one of the other serious outcomes noted above.

All adverse events that do not meet any of the criteria for serious should be regarded as **non-serious adverse events**.

Adverse Event Reporting Period

The study period during which adverse events must be reported is normally defined as the period from the initiation of any study procedures to the end of the study treatment follow-up. For this study, the study treatment follow-up is defined as 14 days following the last administration of study treatment.

Preexisting Condition

A preexisting condition is one that is present at the start of the study. A preexisting condition should be recorded as an adverse event if the frequency, intensity, or the character of the condition worsens during the study period.

General Physical Examination Findings

At screening, any clinically significant abnormality should be recorded as a preexisting condition. At the end of the study, any new clinically significant findings/abnormalities that meet the definition of an adverse event must also be recorded and documented as an adverse event.

Post-study Adverse Event

All unresolved adverse events should be followed by the investigator until the events are resolved, the subject is lost to follow-up, or the adverse event is otherwise explained. At the last scheduled visit, the investigator should instruct each subject to report any subsequent event(s) that the subject, or the subject's personal physician, believes might reasonably be related to participation in this study. The investigator should notify the ethical committee of any death or adverse event occurring at any time after a subject has discontinued or terminated study participation that may reasonably be related to this study.

Abnormal Laboratory Values

A clinical laboratory abnormality should be documented as an adverse event if any one of the following conditions is met:

- The laboratory abnormality is not otherwise refuted by a repeat test to confirm the abnormality
- The abnormality suggests a disease and/or organ toxicity
- The abnormality is of a degree that requires active management; e.g. change of dose, discontinuation of the drug, more frequent follow-up assessments, further diagnostic investigation, etc.

Hospitalization, Prolonged Hospitalization or Surgery

Any adverse event that results in hospitalization or prolonged hospitalization should be documented and reported as a serious adverse event unless specifically instructed otherwise in this protocol. Any condition responsible for surgery should be documented as an adverse event if the condition meets the criteria for an adverse event.

Neither the condition, hospitalization, prolonged hospitalization, nor surgery are reported as an adverse event in the following circumstances:

- Hospitalization or prolonged hospitalization for diagnostic or elective surgical procedures for a preexisting condition. Surgery should *not* be reported as an outcome of an adverse event if the purpose of the surgery was elective or diagnostic and the outcome was uneventful.
- Hospitalization or prolonged hospitalization required to allow efficacy measurement for the study.

- Hospitalization or prolonged hospitalization for therapy of the target disease of the study, unless it is a worsening or increase in frequency of hospital admissions as judged by the clinical investigator.

Recording of Adverse Events

At each contact with the subject, the investigator must seek information on adverse events by specific questioning and, as appropriate, by examination. Information on all adverse events should be recorded immediately in the source document, and also in the appropriate adverse event module of the case report form (CRF). All clearly related signs, symptoms, and abnormal diagnostic procedures results should recorded in the source document, though should be grouped under one diagnosis.

All adverse events occurring during the study period must be recorded. The clinical course of each event should be followed until resolution, stabilization, or until it has been determined that the study treatment or participation is not the cause. Serious adverse events that are still ongoing at the end of the study period must be followed up to determine the final outcome. Any serious adverse event that occurs after the study period and is considered to be possibly related to the study treatment or study participation should be recorded and reported immediately.

Reporting of Serious Adverse Events and Unanticipated Problems

The investigator and sub-investigators report all types of unanticipated problems, adverse events and serious adverse events to the ethical committee within 24 hours of the event. A Serious Adverse Event (SAE) form must be completed by the investigator and send to the EC within 24 hours. The investigator will keep a copy of this SAE form on file at the study site.

Investigators must conform to the adverse event reporting timelines, formats and requirements of the various entities to which they are responsible, but at a minimum those events that must be reported are those that are:

- related to study participation,
- unexpected, and
- serious or involve risks to subjects or others
(see definitions, section 12.1).

If the report is supplied as a narrative, the minimum necessary information to be provided at the time of the initial report includes:

- Protocol number
- Subject number
- A description of the event
- Date of onset
- Current status
- Whether study treatment was discontinued
- The reason why the event is classified as serious
- Investigator assessment of the association between the event and study treatment

Within the following 48 hours, the investigator must provide further information on the serious adverse event in the form of a written narrative. This should include a copy of the completed Serious Adverse Event form, and any other diagnostic information that will

assist the understanding of the event. Significant new information on ongoing serious adverse events should be provided promptly to the MEC, UMMC.

Unblinding Procedures

While the safety of the subject always comes first, it is important to consider if unblinding the study therapy is necessary to ensure a subject's safety. If the SAE is confirmed due to the study therapy, the timeline of reporting is within 24 hours, however, in cases where unblinding was not associated with an SAE, the timeline of reporting is within 1 week.

Medical Monitoring

It is the responsibility of the Principal Investigator to oversee the safety of the study at his/her site. This safety monitoring will include careful assessment and appropriate reporting of adverse events as noted above, as well as the construction and implementation of a site data and safety-monitoring plan (see Section 10 Auditing, Monitoring and Inspecting). Medical monitoring will include a regular assessment of the number and type of serious adverse events.

Protection of Subjects

Complementing the safety measures noted above, additional procedures will be followed to protect the safety of the research subjects. Potential Subjects will be screened for medical illnesses that would preclude the use of methylphenidate. Specifically, these include known allergies to this agent. Subjects selected for the study will be evaluated daily while receiving study drug treatments. AEs will be monitored daily and a study physician will be available at all times to evaluate and treat adverse effects of the medication. On a daily basis, vital signs will be obtained. Significant AEs will result in exclusion from the study (see Clinical Trial Discontinuation Criteria). Subjects will be given a 24-hour emergency number they can call if necessary. The investigator or sub-investigators will clinically follow all subjects who are discontinued due to serious AEs until the AE resolves and becomes completely stable, unless a referral to another physician (i.e. specialist) is clinically indicated or requested by the subject.

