TEST PRODUCT, DOSE, AND ROUTE OF ADMINISTRATION	Bupropion hydrochloride sustained-release (Wellbutrin SR) 150mg once a day for 7 days then 150mg twice a day for 35 days. Taken orally by the subjects.
DURATION OF SUBJECT PARTICIPATION AND DURATION OF STUDY	Subjects will be on study for up to 63 days Screening: up to 7 days(1 week) Treatment: 42days (6 weeks) Follow-up: 14 days (2 weeks) The total duration of the study is expected to be 24 months. 20months for subject recruitment and 4 months for final subject follow-up.
EFFICACY EVALUATIONS	
PRIMARY ENDPOINT	
 Change from baseline International Index of Erectile Function (IIEF-15) score.
SECONDARY ENDPOINTS	
 Mean improvement in scores on the Clinical Global Impression Scale adapted for sexual Function (CGI-SF) Mean improvement in scores on the Arizona Sexual Experience

	
Scale (ASEX)
 
 • Safety and Tolerability
OTHER EVALUATIONS	
 • Montgomery-Åsberg Depression Rating Scale (MADRS- Malay version) • Mini International Neuropsychiatric Interview (M.I.N.I), • Opiate Treatment Index (OTI) • World health organization Quality of Life-Brief Scale (WHOQoL-Brief, Malay version) , • Malay Version of the Golombok-Rust Inventory of Marital State (Mal-GRIMS) • Rapid urine drug test
SAFETY EVALUATIONS	Incidence of adverse events
STATISTICS Primary Analysis Plan	Data will be analyzed using linear mixed-effects model.

TABLE OF CONTENTS	Pg
LIST OF ABBREVIATIONS	3
PROTOCOL SUMMARY	4
INTRODUCTION	9
1. BACKGROUND	9
1.1 Investigational Agent	10
1.2 Overview of Non-Clinical Studies	10
1.3 Overview of Clinical Studies	11
1.4 Risk / Benefit Assessment	11
1.4.1 Dose Rationale	11
1.4.2 Potential Risk	11
1.4.3 Potential Benefit	11
1.4.4 Risk Benefit Ratio	11
2 STUDY RATIONALE	12
3 STUDY OBJECTIVES	12
3.1 Primary Objective	12
3.2 Secondary Objectives	12
4 STUDY DESIGN	13
4.1 Design	13
4.2 Procedure	13
4.3 Project Timetable	14
5 CRITERIA FOR EVALUATION	14
5.1 Primary Efficacy Endpoint	14
5.2 Secondary Efficacy Endpoints	14
5.3 Safety Evaluations	14
6 SUBJECT SELECTION	15
6.1 Study Population	15
6.2 Inclusion Criteria	15
6.3 Exclusion Criteria	15
6.4 Subject Recruitment and Screening	15
7 EARLY WITHDRAWAL OF SUBJECTS	16
7.1 When and How to Withdraw Subjects	16
7.2 Data Collection and Follow-up for Withdrawn Subjects	17
8 STUDY TREATMENTS	17
8.1 Method of Assigning Subjects to Treatment Groups	17

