4.2 Procedure

All the male subjects who attended the methadone maintenance clinic will be approached. Screening data will be reviewed to determine subject eligibility. Subjects who meet all

inclusion criteria and none of the exclusion criteria will be entered into the study. Sexual dysfunction will be measured by CGI-SF, IIEF-15 and ASEX,

Seventy (70) of subjects will be randomized to one of two experimental treatments (35 subjects per group): bupropion hydrochloride sustained or placebo. Bupropion hydrochloride sustained or placebo will be initiated after screening and continued for 42 days of outpatient treatment. Efficacy will be take place at baseline, day 14(week 2), day 28(week four) and day 42 (week 6).

At the end of the 42 days, the continuation of treatment will be depends on the investigator's clinical judgment and End of Medication Evaluation will be perform. Every effort will be made to continue to evaluate all subjects who are randomized even if they decide to discontinue the medication.

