7 EARLY WITHDRAWAL OF SUBJECTS

7.1 When and How to Withdraw Subjects

Subjects will be withdrawn from the study in the following condition:

- Report of clinical significant adverse events felt to be related to study drug
- Failure of subject to adhere to protocol requirements
- Subject withdraw consent or their authorization to use their protected health information
- Subject is too ill to continue with the study procedure
- Deemed by the principal investigator to be in their best interest

Subjects discontinued from the clinical trial will be scheduled for a final evaluation. The investigator or sub-investigators will continue the care, consider alternative treatment or given appropriate treatment referrals for the subjects who withdraw from the study.

All subjects randomized into the study will be included in the final study analyses. Subjects are not dropped from all study activity unless they request not to be contacted or cannot be located for follow-up assessment. Subjects will be informed at the consent session that treatment may be discontinued due to:

- Intolerable side effects;
- Significantly abnormal laboratory values or confirmed with a repeat testing;
- Development or exacerbation of sexual dysfunction;
- Clinical deterioration for any reason or any clinical status that necessitates IP admission;

Reasons why subjects are discontinued from the clinical trial will be documented on the Study Termination Form, along with any referrals that are made. A final safety evaluation will be conducted as soon as possible on all randomized subjects who are discontinued. Every effort will be made to continue to collect data on every randomized subject for the entire study duration regardless of whether or not the subject continues to take study medication, assuming the subject has now withdrawn his/her authorization to obtain such information.

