7.2 Data Collection and Follow-up for Withdrawn Subjects

Even though subjects may be withdrawn prematurely from the study all adverse event data will continue to be collected through 14 days from cessation of study drug (with the subject's permission). Subjects who have study drug discontinued for any reason, but are willing to complete study visits will have all assessments administered and collected. For the final measures, subjects will receive all assessments that were scheduled for the End of Study visit.

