10.7 Visit 6 (week 6) (end of study drug)

Any Adverse Experiences will be recorded. Subject diary for adverse experiences and dosing compliance will be reviewed. Concomitant medications will be reviewed; abbreviated physical examination will be performed, vital signs will be recorded, Urinalysis for illicit drug and electrocardiography will be recorded. Approximately 5ml(1 teaspoon) of blood will be collected for liver function test: AST(GOT) and ALT(GPT). CGI-SF, IIEF15, and ASEX will be completed. CGI-SF, IIEF15, and ASEX will be completed.

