10.8 Early Withdrawal Visit

Any Adverse Experiences will be recorded. Subject diary for adverse experiences and dosing compliance will be reviewed. Concomitant medications will be reviewed; abbreviated physical examination will be performed, vital signs will be recorded, Urinalysis for illicit drug and electrocardiography will be recorded.

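### The visit schedule has no contact after Visit 6 to deliver the 14-day and 28-day safety windows, and the withdrawal visit omits the liver test that section 7.2 implies

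*Combined protocol and SAP*

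**What the plan says.** On the length of follow-up:

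- The Protocol Summary breaks participation into screening, treatment and "Follow-up: 14 days (2 weeks").
- Section 12.2 (Adverse Event Reporting Period) says: "For this study, the study treatment follow-up is defined as 14 days following the last administration of study treatment". The same section requires every adverse event in the study period to be recorded, with specific questioning at each contact.
- Section 7.2 also uses 14 days for withdrawn subjects.
- Section 5.3 defines the primary safety endpoint as serious adverse events up to 28 days after treatment stops.

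On scheduled contacts:

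- Section 10 ends at Visit 6, labelled the end of study drug, and books nothing after it. Appendix 1 also stops there. Its one mark extending to 14 days is in the withdrawal column.
- After the last visit, under Post-study Adverse Event, 12.2 says "the investigator should instruct each subject to report any subsequent event(s) that the subject, or the subject's personal physician, believes might reasonably be related" to the study.

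On early withdrawal:

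- Section 7.2: "subjects will receive all assessments that were scheduled for the End of Study visit".
- Section 10.7 (Visit 6): "Approximately 5ml(1 teaspoon) of blood will be collected for liver function test: AST(GOT) and ALT(GPT").
- Section 10.8 (Early Withdrawal Visit): "vital signs will be recorded, Urinalysis for illicit drug and electrocardiography will be recorded". It mentions no blood sample.
- The withdrawal column of Appendix 1 is blank for blood, urine and ECG.

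On the end of treatment: 8.3.2.2 runs treatment to day 42, while 4.2 says that after 42 days "the continuation of treatment will be depends on the investigator's clinical judgment".

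**The concern.** The incidence of adverse events is the safety evaluation named in the Summary, and serious adverse events are the primary safety endpoint in 5.3. Both depend on someone asking. Under 12.2 the asking happens at contacts, and under 8.8 the diary is brought to study visits. With no contact after Visit 6, neither route operates for completers once they are off drug. What remains in practice is follow-up of events already known, and reports that subjects volunteer because they or their physician suspect a link. That is narrower than all adverse events and will vary from subject to subject.

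For withdrawers, the concern is that staff work from the visit list and the schedule table. Followed as written, 10.8 or Appendix 1 would produce no liver sample at withdrawal, although 7.2 appears to require one.

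**Working it through.** **1. The plan's own total.** The Summary gives up to 7 days of screening, 42 of treatment and 14 of follow-up: 7 + 42 + 14 = 63 days. This reproduces the stated 63.

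**2. Days without a scheduled contact, completers.** Visit 0 is study day 0. Visits follow at 7-day intervals, so Visit 6 is at week 6. (Section 10.5 names Visit 6 rather than Visit 5 as the next visit, so I used the week labels in the section headings.) Two readings are possible:

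- *Visit 6 is treatment day 42.* This matches the label of 10.7 and the day-42 assessment in 4.2. Visit 6 then falls on study day 7 + 42 = 49, and the gap is 63 − 49 = 14 days. 14/63 = 22.2%.
- *Section 10 taken literally.* Drug starts at Visit 1 (10.2), study day 7. Forty-two days of treatment end on study day 7 + 42 = 49, but Visit 6 is on study day 42. The last visit comes 49 − 42 = 7 days before the last dose, and the gap is 63 − 42 = 21 days. 21/63 = 33.3%. Appendix 1 supports this reading: it ticks prescription of study drug at Visits 1 to 6, including Visit 6, and 8.6 packs the drug by the week.

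**3. The 28-day window.** 7 + 42 + 28 = 77 days, which is 77 − 63 = 14 days beyond stated participation. After Visit 6 there are 77 − 49 = 28 days without contact on the first reading, or 77 − 42 = 35 on the second. A single contact 14 days after the last dose would cover 14/28, half of the 5.3 window.

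**4. Early withdrawal.**

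| | AST/ALT | Urine | ECG |
|---|---|---|---|
| Visit 6 (10.7), reached through 7.2 | yes | yes | yes |
| 10.8 | not listed | yes | yes |
| Appendix 1, withdrawal column | blank | blank | blank |

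Footnote 2 of Appendix 1 independently limits post-baseline liver tests to Visits 3 and 6. The urine and ECG blanks rest on the table layout alone. No visit is actually named End of Study, and 7.2 does not say whether the final measures are taken at stopping or at week 6.

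**5. The anchor.** The 12.2 window counts from the last administration. That date is uncertain if treatment can continue beyond day 42 (4.2 against 8.3.2.2), or if Visit 6 precedes the last dose (step 2).

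**The case against.** The strongest reply is that the duty to collect exists even though the visit does not. Section 12.2 requires all adverse events in the study period to be recorded and unresolved ones to be followed. Section 7.2 and the withdrawal column of Appendix 1 extend collection to 14 days for withdrawers. Section 7.1 adds a final safety evaluation, and 13.1 encourages subjects who stop drug to attend the remaining visits. The self-report instruction concerns events after the study and does not replace that duty. Much of this stands. A reader might infer that post-dose events go unmeasured, but the documents do not support that. What is missing is a scheduled, uniform means of carrying out the duty.

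Section 12.2 also describes daily evaluation while subjects receive drug. If done, it would cover the last on-drug week on the literal reading and bring 21 days back to 14. It appears in neither section 10 nor Appendix 1, and it does not reach the off-drug period.

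Other stronger readings also fail:

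- *Liver abnormalities that cause stopping are missed.* Section 7.1 lists "Significantly abnormal laboratory values or confirmed with a repeat testing" among the reasons for stopping treatment. A value that led to stopping has already been measured. At most, an abnormality accompanying some other reason could be missed.
- *An abnormal Visit 6 result cannot be repeated.* The repeat test in 12.2 is not tied to a scheduled visit, and follow-up of unresolved events continues.
- *The comparison is biased toward no harm.* The schedule is the same in both blinded arms, and section 11 plans no between-arm AST/ALT comparison. Lower sensitivity is plausible, but no direction of bias is shown.
- *A countable number of subjects will lack a final liver test.* The documents give no stopping rate, and any count would assume that 7.2 is ignored every time.

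Continuation under 4.2 may simply mean care after the trial. That is plausible, but the text does not say so.

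**Conclusion.** The point holds as a gap between what the protocol requires and what its schedule delivers. For completers, at least 14 of 63 days (22%) have no scheduled contact, and about 21 (33%) on a literal reading of section 10. The 28-day window for the primary safety endpoint runs 14 days past stated participation, also without a contact. Adverse events after the last dose are therefore not actively or uniformly ascertained.

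For early withdrawers, 7.2 conflicts with 10.8 and Appendix 1 over the liver test, and 10.8 conflicts with Appendix 1 over urine and ECG. This rests on taking the End of Study visit to be Visit 6.

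The efficacy analysis is unaffected. The consequence is less complete safety data, which is worth correcting because the remedy is cheap.

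**What to change.** - Add a scheduled adverse-event contact to section 10 and Appendix 1 for every randomised subject at the end of the safety window, asking about all adverse events and not only those thought related. A telephone call is enough for this purpose. It cannot repeat AST/ALT or an ECG, so it is not a means of closing out abnormal results.
- Reconcile the 14-day window (Summary, 7.2, 12.2) with the 28-day window (5.3), so that the contact covers the stated safety endpoint. If both are meant, say which events each covers.
- Make 10.8 and the withdrawal column of Appendix 1 agree with 7.2 and with each other. State which visit End of Study means, and when a withdrawer has those assessments.
- Reconcile 4.2 with 8.3.2.2, and the Visit 1 drug start with the label of Visit 6, so that the last-dose date anchoring the window is clear.

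The cost is one call per subject (70 in all; more if two windows are kept with a contact for each), a 5 ml sample for withdrawers that 7.2 already implies, and text edits. The downside is a little more coordinator time.
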